### **2.7 Contura Multi-lumen Balloon and SAVI strut-adjusted applicator**

See Appendix 2 for detailed figures of the device and Appendix 3 for the device inserts which includes description and use.

## **3. STUDY DESIGN**

This multiple site, prospective, non-randomized phase II study has been designed to determine the safety of delivering APBI with a brachytherapy applicator in a short course, 2-3 day fashion.

Data collected during this study will include baseline patient demographics, information related radiation therapy treatment delivery, toxicities, cosmetic outcomes and recurrence data. The patient's follow-up data will be collected during the patient's standard follow-up visits. All patients will be asked to return for clinic visits for a minimum of 2 years. The investigator will continue to review and collect data from the patient's medical record for disease status until the study is completed. This information will be collected to help in data analysis for the secondary objective and resolve any queries that may arise during data analysis and for publication.

### **3.2 Duration of Study**

The duration of the study will be 6 years. Three years to ensure sufficient patient accrual, an additional 2 years for follow up and data analysis.

#### **4. STUDY OBJECTIVES**

##### **4.1 Primary Objective**

To determine the toxicity rate with shorter courses of APBI delivered with a breast brachytherapy applicator.

##### **4.2 Secondary Objectives**

4.2.1.1 To determine the 3-year actuarial local control rate with abbreviated APBI.

4.2.1.2 To assess the rate of excellent or good cosmesis at 2-years after shorter courses of APBI and to identify co-variants associated with and predictive of poor cosmetic outcome in women treated with an overnight treatment course of APBI.

#### **5. STUDY ENDPOINTS**

##### **5.1.1 Primary Endpoint**

The treatment will be considered unsafe if a 2-year serious toxicity rate exceeding 10% cannot be excluded with the 95% interval. Serious toxicity in this study is defined as toxicity greater than grade 2 using CTCAE v4.0 criteria. In a cohort of 200 patients, there should be 11 or fewer serious toxicities to exclude a rate of 10% using the upper limit of the 95% confidence interval.

##### **5.1.2 Secondary Endpoints**

5.1.2.1 We expect that estimated 3-year local control rate (using Kaplan-Meier method) should be greater than 95% (corresponding to a 3-year local failure rate of 5% or lower). We will assess 3- year estimates of local control using the Kaplan-Meier method.

5.1.2.2 The percentage of patients with good/excellent cosmetic results at 2-years should exceed 80%.

### **5.1.3 Cosmesis**

The percentage of patients with good/excellent cosmetic results at 2-years should exceed 80%.

## **6. STUDY POPULATION**

200 women with early stage breast cancer (TIS, T1-2, N0) removed with breast conserving surgery achieving a negative pathologic margin may be enrolled.

### **6.1 Inclusion Criteria**

- 6.1.1 Must sign informed consent
- 6.1.2 Female age 45 or older at diagnosis
- 6.1.3 Surgical treatment of the breast must have been lumpectomy. The margins of the resected specimen must be histologically free of tumor (negative surgical margins per NSABP criteria).
- 6.1.4 On histologic examination, the tumor must be DCIS and/or invasive breast carcinoma.
- 6.1.5 For patients with invasive breast cancer, an axillary staging procedure must be performed [either SNB alone or axillary dissection (with a minimum of six axillary nodes removed), and the axillary node(s) must be pathologically negative]. Patients  $\geq 70$  with ER+ tumors no greater than 2 cm do not require axillary evaluation, but MUST be clinically node negative on examination and all available imaging (clinical N0).
- 6.1.6 The T stage must be Tis, T1, or T2. If T2, the tumor must be  $\leq 3.0$  cm in maximum diameter.
- 6.1.7 Estrogen receptor positive tumor and/or progesterone receptor positive tumor (not applicable to DCIS).

### **6.2 Exclusion Criteria**

- 6.2.1 Age  $< 45$  at diagnosis (regardless of histology)
- 6.2.2 Pregnant or breast-feeding
- 6.2.3 Active collagen-vascular disease (patients not on medication AND ESR $<20$  AND CPK in normal range are eligible for study)
- 6.2.4 Paget's disease of the breast
- 6.2.5 Prior history of DCIS or invasive breast cancer
- 6.2.6 Prior breast or thoracic RT for any condition
- 6.2.7 Multicentric carcinoma (DCIS or invasive)
- 6.2.8 Synchronous bilateral invasive or non-invasive breast cancer
- 6.2.9 Surgical margins that cannot be microscopically assessed or that are positive
- 6.2.10 Positive axillary node(s)
- 6.2.11 T stage of T2 with the tumor  $> 3$  cm in maximum diameter or a T stage  $\geq 3$
- 6.2.12 Estrogen receptor negative and progesterone receptor negative tumor

6.2.13 Any of the dosimetric treatment criteria as defined in Section 9.7 have not been met. Patients who become ineligible due to inability to meet dosimetric criteria should not receive treatment as defined in this protocol and will come off the study; any subsequent adjuvant radiation will be delivered at the discretion of the treating physician.

## 7. STUDY SCHEDULE

### 7.1 Screening and Enrollment

Prior to enrollment in the study, potential participants will be evaluated to determine eligibility. The patient will have undergone standard lumpectomy surgery to remove the tumor. The surgery must have provided negative surgical margins using the NSABP definition.

The investigator will explain the study purpose, procedures, and patient responsibilities to the potential participant. The participant's willingness and ability to meet the follow up requirements will be evaluated. Written informed consent will be obtained from all potential study patients prior to participation.

To register eligible patients on this study, each site will contact Rutgers Cancer Institute of New Jersey's OHSR Registration Desk [contact] and [contact] the signed and dated eligibility checklist, completed signature page of the consent form and additional source documents if requested by OHSR. Once the OHSR Registration Desk verifies eligibility and properly executed consent, a unique patient study number will be issued. The patient will not be identified by name. This is the point that the patient is considered on study. **Patients will not start protocol treatment prior to registration.**

### 7.2 Applicator Placement

The applicator will be placed using ultrasound guidance. Applicator refers to any device used to deliver brachytherapy on this study, including individual 6F catheters, the SAVI applicator, and the Contura MLB applicator. The balloon of the Contura MLB is inflated with a saline/contrast mixture (maximum of 2-3% contrast) to fill the cavity. The balloon will remain inflated throughout the duration of the radiation and will be removed after the last fraction. The SAVI device will be deployed fully using the turn-style and will remain open until the last fraction, when it can be collapsed and removed. Following applicator placement, a treatment planning CT scan must be performed to evaluate the patient for skin spacing, symmetry and applicator conformance.

### 7.3 Treatment Planning

CT imaging is mandatory for treatment planning. Standard treatment planning guidelines for APBI will be employed. CT-based 3-D brachytherapy treatment planning will be conducted using commercially available software and equipment. The treatment will be performed using available high dose rate (HDR) brachytherapy. (Refer to Section 9 for specific details regarding dosimetric guidelines and quality assurance criteria.)

### 7.4 Prescription Delivery and Brachytherapy Treatment

In general, brachytherapy should start between 1-5 days after balloon placement.

Dose - 7.50 Gy X 3 = 22.5 Gy delivered in 3 fractions over 2-3 days

In addition, to confirm that the patient's position is identical to the position of the initial planning CT, the applicator's inflation status and rotational motion will be verified prior to each fraction. If any problems are found during the confirmation check, refer to the Instructions for Use (refer to Appendix 3 or the applicator package for the most recent version). All treatments will be completed using commercially available HDR and Ir-192 radioactive sources.

Note: A minimum of 6 hours must occur between dose fractions.

### **7.5 Applicator Removal**

The applicator removal should be scheduled after completing the treatment. The applicator should be removed using standard technique and the applicator exit/entrance site should be dressed according to standard medical practice.

### **7.6 Post-Applicator Removal Follow-Up Visits**

The patient should be seen according to the standard of care for follow-up office visits. The first post-RT office visit should occur between 2-8 weeks post-treatment, then at least annually for years 1 and 2 post- RT. (see Appendix 1). Mammography should be performed according to institutional standards of practice and is generally performed as a baseline 6-12 months after brachytherapy and repeated annually.

The occurrence of adverse events, including toxicities, second primary cancers, and deaths (on therapy or prior to evidence of disease progression), will be monitored continuously. Recurrences and new cancers detected using standard imaging will be documented. Biopsy and additional treatment will also be documented, if applicable. Cosmetic grading, seroma formation, infection, fibrosis, fat necrosis, pain, telangiectasia, must be evaluated and reported at each visit.

### **7.7 Study Completion**

An exit case report form must be completed for all study participants.

#### **7.7.1 Patient Completion**

A patient is considered to have completed the study if the follow-up examinations were completed through year 2.

#### **7.7.2 Patient Discontinuation**

7.7.2.1 A patient may be discontinued from the study at the discretion of the investigator if the patient's condition deteriorates or if the investigator decides that continuing in the study may be detrimental to the health or welfare of the patient.

7.7.2.2 Voluntary withdrawal from the study by the patient (note: voluntary withdrawal may occur at any time during the study and will not affect the patient's future medical treatment or benefits)

#### **7.7.3 Patient Lost to Follow-Up**

A patient may be lost to follow-up for non-treatment related reasons. Reasons for loss to follow-up include, but are not limited to:

7.7.3.1 Patient has moved from the area

7.7.3.2 Patient is unwilling or unable to return for follow-up

**8. Brachytherapy Applicators**

**8.1 Device Description**

**8.1.1 Applicator and Tray**

Several vendors provide 6 F catheters for soft tissue implantation and any of these can be used for the purpose of a multicatheter implant. Catheters can be packaged individually or bundled and are shipped sterile by vendors or can be sterilized at the provider site. The Contura MLB and SAVI applicators are used to position tissue and radioactive sources during breast brachytherapy treatments. They each consist of a multi-lumen tube, while the Contura has an inflatable balloon assembly at its distal end and the SAVI has peripheral struts that deploy/expand. The SAVI device is available in four sizes, 2.4 (mini), 3, 4, and 5 cm diameters.

The Contura MLB is available with two balloon sizes; a variable diameter ranging from 4-5 cm or 5-6 cm. The balloon fill volumes are listed below:

4-5 cm BALLOON		
Fill Volume (cc)	Volume	Diameter (mm)
33		40
35		41
37		42
39		43
42		44
44		45
47		46
50		47
52		48
55		49
58		50

5-6 cm BALLOON		
Fill Volume (cc)	Volume	Diameter (mm)
40		40
42		41
44		42
47		43
49		44
51		45
54		46
57		47
59		48
63		49
66		50
Fill Volume (cc)	Volume	Diameter (mm)
69		51
73		52
77		53
80		54
84		55
88		56
93		57
96		58
102		59
108		60

The applicator trays are supplied in sterile packaging and come packaged with the equipment needed to implant the applicator. The Instructions for Use and chart labels are also provided in the applicator tray.

**8.1.2 Afterloader Connector Accessories**

Standard adapters or transfer tubes needed to connect the applicators to the various commercially available HDR machines are available from the HDR manufacturers.

**8.2 Physics Training**

It is the responsibility of each participating institution to have a thorough understanding of the proper placement, management and removal of the applicators prior to study participation and that proper and effective quality assurance procedures are followed for each case. Physics training is available (by the manufacturer of the device) and is strongly recommended.

## 9. TREATMENT PLANNING & DOSE DELIVERY

### 9.1 Imaging

A treatment planning CT scan with the patient in an easily reproducible position with the applicator in place will be required for assessing appropriateness for treatment and treatment planning. The CT scan should at least include 3 cm both cephalad and caudal to the applicator for proper assessment of dose delivery. A CT scan thickness of  $\leq 0.3$  cm should be employed. The following structures will be contoured: (a) applicator surface, (b) planning target volume for evaluation (PTV\_EVAL) – (see below), (c) trapped air and/or fluid, (d) skin surface, and (d) aspect of the closest rib that is adjacent to the balloon. The target volumes and normal tissue structures should be outlined on all CT cuts when appropriate.

It is critically important that at the time of the planning CT, the rotational orientation of the applicator is documented so that prior to each treatment the proper orientation can be reproduced. It is suggested that the shaft orientation line position be noted and a skin mark or the skin incision be used for consistent rotational positioning. Additionally, a dummy marker wire can be placed into lumen #1 to further document orientation of the device for proper CT planning or multiple dummy wires placed in each lumen for identification.

### 9.2 Target Volumes

As the applicator moves with the target, compensation for variability of treatment set-up and breathing motion is not needed; the planning target volume for evaluation (PTV\_EVAL) = clinical target volume (CTV) = planning target volume (PTV). Therefore, within this protocol, only the PTV\_EVAL will be referenced. The PTV\_EVAL will be delineated as the breast tissue volume bounded by the uniform expansion of the balloon radius in all dimensions by 10 mm less the balloon volume and limited to 5 mm from the skin surface and by the posterior breast tissue extent (chest wall and pectoralis muscles are not to be included) as long as dosimetric criteria can be met.

When determining dose coverage of the PTV\_EVAL to assure compliance with dose requirements, as outlined in Section 9.7, the volume of trapped air/fluid must be accounted for as it displaces a percentage of the target beyond 1 cm from the balloon surface. The area of trapped air/fluid will be contoured at each level, a total volume obtained and the percentage of the PTV\_EVAL that it displaces calculated. When determining the PTV\_EVAL dose coverage, this displaced percentage must be subtracted. For example, if the percentage of PTV\_EVAL displaced by trapped air/fluid is calculated to be 5-10%, then to comply with criteria, the dose coverage must be at least 95% of the PTV\_EVAL receiving 90% of the prescribed dose. If the percentage of PTV\_EVAL displaced by trapped air/fluid is greater than 10%, then it is not possible to achieve acceptable dose coverage and the patient will not be enrolled.

### 9.3 Treatment Planning

Radioactive source location, number of lumens, number of positions and dwell times are at the discretion of the physician and will be determined by High Dose Rate CT-based 3D treatment planning to produce the optimal conformal plan in accordance with volume definition and dose requirements. The treatment plan used for each patient will be based on analysis of the

volumetric dose including dose-volume histogram (DVH) analyses of the PTV\_EVAL and critical normal tissues.

#### **9.4 Determination of Appropriateness for Treatment**

Appropriateness for treatment will be based on the ability to achieve the dosimetric goals. However, three basic parameters can be used for determining whether the geometric placement will provide the ability to achieve the dosimetric goals. These basic parameters include: (a) tissue-device conformance, (b) device symmetry, and (c) minimal device-skin distance. As a result of the dose shaping capabilities of the SAVI and Contura MLB applicators, minimum requirements for these geometric parameters are case dependent. The general rules are outlined as follows:

##### **9.4.1 Tissue-Device Conformance**

Ideally, the lumpectomy cavity surface should be in direct contact with the entire balloon surface or with the struts of the SAVI applicator, assuring maximum prescription dose coverage of the PTV\_EVAL. Frequently air and/or fluid will be identified between the lumpectomy cavity and applicator surface. Either as a result of an irregular cavity shape or because the air/fluid is trapped, a less than ideal conformance results and “pushes” a percentage of the PTV\_EVAL beyond the prescription isodose line coverage. To determine the significance of the trapped air/fluid, these volumes will be contoured and used in calculating PTV dose coverage (Section 9.7). Typically, when the volume of trapped air/fluid is < 10% of the PTV, acceptable dose coverage can be achieved. No adjustment is needed if the volume is less than 5%. For displaced volumes that are 5-10% fo the PTV, the coverage constraint must be at least 95% of the PTV\_EVAL receiving 90% of the prescribed dose

##### **9.4.2 Balloon and Strut Symmetry**

The symmetry of the balloon surface or applicator struts with respect to the central lumen can have, particularly for the older single lumen balloon devices, negative effects on the dosimetric coverage of the PTV, as well as on the volume of tissue receiving more than 200% of the prescribed dose. Such asymmetry, when existent, can be corrected with the dose shaping capabilities of the multi-lumen devices. The success and degree of correction will depend on the degree of asymmetry and should be image-verified for consistency every fraction. Case-by case discretion is needed in these instances and should be discussed with the study investigators if needed.

### **9.4.3 Minimal Balloon/Strut Surface-Skin/Rib Distance**

In this unique dose escalation trial, strict attention to skin and rib dose is critical. For the purpose of this trial, it is required that the skin and rib maximum dose is kept as low as possible, preferably at or under 100% of prescription dose. However, point maximum doses  $\leq 120\%$  of the prescription dose are allowed.

### **9.5 Dose Prescription and Dose Escalation**

Dose fractionation scheme:

Dose level – 7.50 Gy X 3 = 22.50 Gy delivered in 3 fractions over 2-3 days

Note: A minimum of 6 hours must occur between dose fractions; a fraction interval greater than 8 hours is recommended.

### **9.6 Dose Delivery**

Treatment utilizing the brachytherapy device should begin within 1-5 days from the acquisition of the planning CT. High dose-rate brachytherapy treatment delivery will be employed, low dose-rate dose delivery will not be allowed. The applicator will remain expanded throughout the treatment course.

Prior to each treatment, it is necessary to assure:

Continued integrity of the applicator throughout treatment, as determined by ultrasound or x-ray/CT performed prior to each delivered fraction and evaluated for any change in diameter. These should be compared to a similar study performed at the time of treatment planning. If a change in applicator geometry is noted, this should be addressed prior to additional treatment.

The patient's position in which the planning CT was obtained is reproduced prior to each fraction.

To assure proper orientation of the device throughout treatment, the orientation line will be identified and the proper alignment, as compared to the alignment at the time of planning, will be verified and corrected if any rotational deviation is seen prior to each treatment.

## 9.7 Quality Assurance of Dose Distribution

After target volumes have been delineated, each treatment plan shall be developed based on the dose distribution parameters listed below.

### 9.7.1 Acceptable

- 9.7.1.1 Dose volume histogram analysis of target coverage goal is  $\geq 90\%$  of the prescribed dose covering  $\geq 90\%$  of the PTV\_EVAL. The volume of trapped air/fluid will be accounted for using methodology described in Section 9.4.1. A 5% adjustment will be necessary therefore confirming that  $\geq 95\%$  of the prescribed dose covering  $\geq 90\%$  of the PTV\_EVAL.
- 9.7.1.2 Maximum skin dose will be reduced to as low as achievable while satisfying all dose parameters with a target constraint of no greater than 100% of prescription dose. A relaxation constraint not exceeding 120% of the prescribed dose is allowed.
- 9.7.1.3 Maximum rib dose will be reduced to as low as achievable while satisfying all dose parameters with a target constraint of no greater than 100% of prescription dose. A relaxation constraint not exceeding 120% of the prescribed dose is allowed.
- 9.7.1.4 The volume of breast tissue receiving 150% (V150) of the dose should be reduced to as low as achievable while satisfying all dose parameters, but should not exceed 40 cc.
- 9.7.1.5 The volume of breast tissue receiving 200% (V200) of the dose should be reduced to as low as achievable while satisfying all dose parameters, with a target constraint of 15 cc. The V200 should not exceed 17 cc.
- 9.7.1.6 For multicatheter implants, an additional metric of homogeneity, the Dose Homogeneity Index (or DHI) must be at least 0.75. The DHI is represented by the volume ratio  $(1 - V150/V100)$ , where V150 and V100 represent 150% of prescription dose and 100% of prescription dose respectively.

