1.5.2.12 Estrogen receptor negative and progesterone receptor negative tumor

1.5.2.13 If any of the dosimetric treatment criteria as defined in Section 9.7 have not been met. Patients who become ineligible due to inability to meet dosimetric criteria should not receive treatment as defined in this protocol and will come off the study. Any subsequent adjuvant radiation will be delivered at the discretion of the treating physician.

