### 9.7.2 Unacceptable

- 9.7.2.1 Dose volume analysis of the target volume confirms  $< 90\%$  of the prescribed dose covering  $< 90\%$  of the PTV\_EVAL. The volume of trapped air/fluid will be accounted for using methodology described in Section 9.4.1.
- 9.7.2.2 Maximum skin dose exceeds 120% of the prescribed dose.
- 9.7.2.3 Maximum rib dose exceeds 120% of the prescribed dose.
- 9.7.2.4 The volume of breast tissue receiving 150% (V150) of the dose exceeds 40 cc.
- 9.7.2.5 The volume of breast tissue receiving 200% (V200) of the dose exceeds 17 cc.
- 9.7.2.6 DHI  $< 0.75$  (for multicatheter cases).

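### Section 9.7.1.1 raises the dose threshold to 95% for trapped air or fluid, where the method it cites (9.4.1, and also 9.2) raises the volume threshold

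*Combined protocol and SAP*

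**What the plan says.** The base coverage goal in Section 9.7.1.1 is at least 90% of the prescribed dose to at least 90% of the PTV_EVAL. For trapped air or fluid it refers to the method in Section 9.4.1. It then adds: "A 5% adjustment will be necessary therefore confirming that" at least 95% of the dose covers at least 90% of the PTV_EVAL.

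Section 9.4.1 puts the 95% on volume: "For displaced volumes that are 5-10% fo the PTV, the coverage constraint must be at least 95% of the" PTV_EVAL, at 90% of the prescribed dose. It waives the correction for small displacement: "No adjustment is needed if the volume is less than 5" percent. Section 9.2 gives the same rule: if displacement is "calculated to be 5-10%, then to comply with criteria, the dose coverage must be at least 95% of the" PTV_EVAL, again at 90% of dose. Section 9.2 also gives the reason. Trapped air or fluid pushes part of the target out of coverage, so the displaced percentage is subtracted.

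The reject rule, 9.7.2.1, opens "Dose volume analysis of the target volume confirms" and gives only the unadjusted 90%/90% limits. It then says: "The volume of trapped air/fluid will be accounted for using methodology described in Section 9.4.1".

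Exclusion 1.5.2.13 applies "If any of the dosimetric treatment criteria as defined in Section 9.7 have not been met", and 6.2.13 says the same. Such a patient does not receive protocol treatment and comes off study.

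**The concern.** Trapped air or fluid is a problem of displaced volume, so the correction belongs on the volume threshold. Two sections put it there. The third cites one of those two as its source and then moves the correction to dose. Raising the dose required over an unchanged 90% of the volume does nothing about the part of the target that has been displaced.

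The error sits in the list of acceptance criteria, which is the list the exclusion criteria name. The trial has several sites. One site may apply the sentence printed in 9.7.1.1, while another follows the pointer to 9.4.1 or works from 9.7.2.1. Those sites could accept or remove the same borderline plan differently. The cross-references do not settle the matter, because 9.4.1 sends the coverage calculation back to Section 9.7.

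**Working it through.** **1. The rules side by side**

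| Section | Dose threshold | Volume threshold | Condition stated there |
|---|---|---|---|
| 9.7.1.1, base goal | ≥90% | ≥90% | none |
| 9.2 | 90% | ≥95% | 5–10% displaced |
| 9.4.1 | 90% | ≥95% | 5–10% displaced; no correction below 5% |
| 9.7.1.1, adjusted | ≥95% | ≥90% | none |
| 9.7.2.1, reject | <90% | <90% | points to 9.4.1 |

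**2. Apply the cited method to the base goal.** The volume threshold becomes 90% + 5% = 95% and the dose threshold stays at 90%. Section 9.7.1.1 prints 95% of dose and 90% of volume, so its adjusted criterion does not follow from the method it names.

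**3. Compare the two tests.** Write D95 and D90 for the percentage of prescribed dose received by 95% and 90% of the PTV_EVAL. CRF #2 records these as items 15b and 15c.

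- 9.4.1 test: D95 ≥ 90. Volume allowed below 90% of dose: 100 − 95 = 5%.
- 9.7.1.1 test: D90 ≥ 95. Volume that may be below 90% of dose: up to 100 − 90 = 10%, the same as under the unadjusted goal.

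**4. Illustration with the geometry in Section 2.6** (spherical balloon of 4.5 cm diameter, prescription at 1 cm, inverse-square fall-off). The shell runs from 2.25 to 3.25 cm, and dose at radius r is s × (3.25/r)², where s scales the plan relative to prescription.

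- Radius enclosing a fraction f of the shell: r³ = 2.25³ + f(3.25³ − 2.25³) = 11.391 + 22.938f.
- f = 0.95: r = 3.213 cm, so D95 = 102.29% × s.
- f = 0.90: r = 3.176 cm, so D90 = 104.72% × s.
- s = 1: D95 = 102.3% and D90 = 104.7%. Both tests pass.
- s = 0.89 (Plan A): D95 = 91.0%, which meets 9.4.1; D90 = 93.2%, which fails 9.7.1.1.
- The tests disagree for s from 0.90/1.0229 = 0.880 to 0.95/1.0472 = 0.907.
- At s = 0.907, where 9.7.1.1 is just met, D95 = 0.907 × 102.29% = 92.8%, already above 90%. In this geometry every disagreement is therefore a plan that meets 9.4.1 and fails 9.7.1.1.

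**5. The other direction, by assumption.** Take Plan B with D95 = 88% and D90 = 96%. It fails 9.4.1 (88 < 90) and meets 9.7.1.1 (96 ≥ 95). At 5–10% displacement it is acceptable under 9.7.1.1 and unacceptable under 9.7.2.1 read with 9.4.1. The pair is assumed, not derived from the sphere.

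The sphere contains no trapped air. Steps 4 and 5 show that the tests differ and say nothing about how often.

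**The case against.** The strongest reply is that this is a drafting slip which the protocol largely resolves. The sentence before it points to 9.4.1, 9.7.2.1 repeats the pointer, and 9.2 and 9.4.1 agree. A careful reader who follows the pointer finds the intended rule, including the 5–10% band. That correctly identifies which text is wrong, but it does not remove the problem. The pointer is followed by an explicit and different threshold, in the list that decides eligibility.

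The second reply concerns direction, and it stands. In the sphere, 9.7.1.1 is always the stricter test, so the modelled harm is wrongly removing a patient, not accepting an under-covered plan. Plan B needs a fall of 96 − 88 = 8 points between D90 and D95, against 104.7 − 102.3 = 2.4 points in the sphere at full prescription. Nothing in the documents shows that such a plan arises. A model without trapped air cannot rule it out either.

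Third, the 9.4.1 rule is not itself full compensation. Subtracting the displaced percentage as 9.2 directs, 95% nominal coverage becomes 95 − 5 = 90% at the low end of the band and 95 − 10 = 85% at the high end. The 5% in step 3 is therefore a limit on the unadjusted histogram, not on the tissue finally under-dosed. This qualifies the contrast but does not reconcile the two rules.

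Finally, one can argue that 9.7.2.1 needs no edit because it already defers to 9.4.1. Strictly that is so. Stating the threshold there is still worthwhile, since the conflict arose where a threshold was printed beside that same pointer.

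**Conclusion.** The concern holds. The last sentence of 9.7.1.1 contradicts the method it cites and the matching rule in 9.2, and the volume version is the one consistent with the stated physical reason. The tests are not equivalent, so the accept and reject rules in Section 9.7 use different adjusted thresholds.

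The practical size is limited. Only plans with 5–10% displacement and borderline coverage should be classified differently, unless a site applies the printed sentence to every plan. In the sphere model, borderline means plans scaled to between 0.880 and 0.907 of prescription. The documents do not give the number of patients involved, and it is probably small. The unadjusted 90/90 goal, the skin, rib, V150 and V200 limits and the rule of at most 11 serious toxicities in 200 patients are unaffected. The textual conflict rests on no modelling assumption; the illustration assumes the Section 2.6 geometry, and Plan B is an assumed pair. The sponsor should correct this because it is an error in an eligibility criterion and is cheap to fix.

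**What to change.** Replace the last sentence of 9.7.1.1 with:

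> If trapped air/fluid displaces 5–10% of the PTV_EVAL, ≥95% of the PTV_EVAL must receive ≥90% of the prescribed dose; below 5% no adjustment applies.

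Make 9.7.2.1 match:

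> Unacceptable if <90% of the PTV_EVAL receives 90% of the prescribed dose, or <95% when trapped air/fluid displaces 5–10%.

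The cost is one sentence, one matching clause and a note to sites. No new data are needed. CRF #2 already records dose to 95% and to 90% of the PTV_EVAL (items 15b and 15c), the air/seroma volume (item 8) and the PTV_EVAL volume (item 12). Treated patients can therefore be checked against either test. Patients removed at planning can be checked only if the planning part of that form was completed for them.
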